7.1.2. Rationale for Starting Dose

The initial dose in this study is based on a thorough review of GLP toxicology studies in both rat and dog models, as well as review of the initial human data from the solid tumor study.

In these non-clinical studies, TP-0184 was administered PO daily for 28 days to rats and dogs in GLP toxicology studies. The severely toxic dose in 10% of rats (STD10) was greater than

150 mg/kg or 900 mg/m² body surface area (BSA), and in the dogs the HNSTD was 5 mg/kg or 100 mg/m² BSA. Given these data, the dog was considered the more sensitive species and per FDA and ICH guidance, the recommended safety approach of taking 1/6th of the HNSTD in dogs (16.7 mg/m²) was calculated to determine an equivalent starting dose in humans of 30 mg/day.

At the start of this study, a Phase 1 first-in-human study exploring escalating dose levels of TP-0184 in patients with advanced solid tumors had already been initiated with a starting dose of 30 mg QD for 21 days. Subsequently, dosing was changed to once weekly, with a starting dose of 60 mg once weekly for 4 weeks (Amendment 2, 12 Sep 2019). The most common side effects, regardless of causality, were gastrointestinal (nausea, vomiting) and fatigue. There were no clinically significant trends of hepatic or cardiac toxicity and the safety profile was considered favorable. Preliminary PK analysis suggested dose-related increases in systemic exposure with increasing dose and longer elimination t_{1/2} than projected from preclinical PK data. Refer to the TP-0184 Investigational Brochure for additional information.

For the current study, a daily dosing regimen of TP-0184 daily for 28 days, without a break, is proposed. This is driven by underlying pharmacological considerations of the target which suggests continuous drug coverage/inhibition to achieve optimal activity/efficacy. However, given the longer elimination t_{1/2} observed in an ongoing first in man solid tumor study (TP-0184-101 study), a lower starting dose of 20 mg/day is proposed, to allow for continuous dosing with a 2.25-fold safety factor built in between the proposed starting dose and the 60 mg/day dose in TP-0184-101 study in which there was acceptable tolerability. Additionally, cardiac and other safety monitoring is included in the protocol for risk mitigation and to ensure ultimate safety of the patients ([Section 12.1.5.4.2](#)).

In summary, both the preclinical safety data and the ongoing clinical experiences in the TP-0184-101 study support the proposed continuous once-daily dosing regimen at 20 mg/day for this study.

7.1.3. Phase 2 – Dose Expansion

Phase 2 will determine the preliminary efficacy of TP-0184 in an expansion phase of up to 60 patients.

Preliminary efficacy as assessed by response rate will be monitored using the Bayesian posterior probability to optimize the enrollment with Bayesian stopping rules.

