7.3.2. Description of Dose Escalation Study

7.3.1. Phase 1 Dose Escalation

Dose escalation will be performed using a design based on a 2-parameter BLRM ([Neuenschwander 2008](#)). The BLRM method will be applied along with the escalation with overdose control (EWOC) principle to control the risk of exposing patients to toxic doses ([Babb 2013](#)). Based on this principle, a dose level will be considered safe if the probability of excessive toxicity (ie, the probability of a DLT rate over 33% is no greater than 25%). The MTD with estimated posterior probability of a DLT within target toxicity interval (16%, 33%) among the admissible doses fulfilling EWOC is determined by BLRM. The MTD is estimated based on observed DLTs.

The use of Bayesian adaptive models for Phase 1 studies has been advocated by the European Medicines Agency's guideline on clinical trials in small populations ([European Medicines Agency, 2016](#)).

The actual dose level to be tested in the next cohort will be chosen based on the above risk assessment, using the BLRM method. The dose recommended by the BLRM method will be treated as guidance and will be integrated with a clinical assessment of the safety adverse event information and review of clinical data, including above safety and PK data. Intermediate doses between planned dose levels may be SDP Oncology explored based on safety consideration after discussion and concurrence with SRC members and SDP Oncology clinical team. The BLRM method estimates the MTD by updating the probability of observing a DLT for each dose level in the study as DLT information becomes available. An additional cohort with a different dose schedule may be considered based on clinical judgment supported by medical observations.

Procedures for close monitoring of the DLT period and entire study have been established ([Section 12.1](#), [Section 14.1](#)). In addition, an SRC will conduct scheduled meetings and will provide safety oversight of the patients, determine DLTs, and guide escalation and dose decisions ([Section 7.3.3](#)).

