7.3.3. Safety Review Committee

The SRC will consist of the Investigators, the Safety Lead, the Statistician, and the Medical Monitor, and a cardiologist consultant. The SRC will conduct scheduled meetings and will provide safety oversight of the patients, determine DLTs, and guide escalation and dose decisions. The SRC will meet after all patients in the newly escalated cohort have completed the DLT evaluation period and before proceeding with the next cohort at a higher dose level.

The SRC will review and assess all available safety data from each cohort, together with available PK and pharmacodynamic data, to determine the escalation to the next dose level cohort. The SRC will also conduct unscheduled meetings on an as needed basis to review other information that may be relevant to the conduct of this study or safety of the patients.

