7.3.4. Phase 1 Study Stopping Rules

Dose escalation can be stopped earlier by a joint decision from the SDP Oncology clinical team and the Investigators during a SRC meeting, by considering the model estimations and a global assessment of the safety, PK, pharmacodynamics, and preliminary activity data.

The following safety event will trigger a temporary suspension of patient enrollment to study treatment:

- The posterior probability of target toxicity at each dose level exceeds 50% and is the highest among potential dose levels.

Based on the safety review by the SRC members and the SDP Oncology clinical team, it will be determined whether the study may continue (with or without a protocol amendment) or if it must be terminated.

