13.1.1. Determination of Sample Size

13.1.2. Phase 1

The exact sample size for Phase 1 (dose escalation part) cannot be specified in advance due to the dynamic features of BLRM study design. Approximately 30 patients are planned to be enrolled in Phase 1.

13.1.3. Phase 2

A total of 10 to 60 patients will be enrolled into Expansion Phase 2. After the first 10 enrolled patients are evaluable for efficacy (Efficacy Evaluable Analysis Set), response rate monitoring using Bayesian posterior probability will be performed. If posterior probability of response rate less or equal than 5% is greater than 90% ($\text{Prob } (\theta \leq 0.05) > 0.90$), the study may be stopped for futility; if posterior probability of response rate greater or equal than 20% is greater than 80% ($\text{Prob } (\theta \geq 0.2) > 0.80$) during study enrollment, SDP Oncology has the option to stop the enrollment of Phase 2 and trigger subsequent clinical development of TP-0184. If neither criterion is met, it will continue to more fully characterize the response rate in a total of approximately 60 efficacy evaluable patients. If posterior probability of response rate greater or equal than 20% is greater than 50% ($\text{Prob } (\theta \geq 0.2) > 0.50$) at the final analysis, the current study will be considered to be successful.

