13.1.8.4. Phase 1 DLT Analysis

The DLT will be summarized by dose level using DAS for patients in Phase 1. By-patient listing of the DLTs will also be provided.

13.1.9. Phase 2

Bayesian posterior probability of response rate will be estimated continuously. The study may be stopped early for futility ($\text{Prob}(\theta \leq 0.05) > 0.90$) or efficacy ($\text{Prob}(\theta \geq 0.2) > 0.80$) during the enrollments starting from 10 enrolled efficacy evaluable patients. Study will be considered to be successful if $\text{Prob}(\theta \geq 0.2) > 0.50$ at the final analysis ($N = \sim 60$).

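### Phase 2 treats up to 60 patients at one dose with numeric monitoring of response only: no aggregate toxicity threshold pauses accrual, and no SRC review point is stated for Phase 2.

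*Protocol*

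**What the plan says.** - **Response monitoring.** Protocol 7.1.3 states: "Preliminary efficacy as assessed by response rate will be monitored using the Bayesian posterior probability to optimize the enrollment with Bayesian stopping rules". Section 13.1.3 sets the criteria, applied once 10 patients are evaluable for efficacy: Pr(θ ≤ 0.05) > 0.90 for futility and Pr(θ ≥ 0.20) > 0.80 for efficacy. Otherwise: "If neither criterion is met, it will continue to more fully characterize the response rate", in about 60 evaluable patients. Section 13.1.9 adds: "Bayesian posterior probability of response rate will be estimated continuously". Here θ is the response rate throughout.
- **Toxicity-based suspension.** One rule exists, in 7.3.4 and again in 13.1.8.3, both headed as Phase 1 stopping rules: "The posterior probability of target toxicity at each dose level exceeds 50% and is the highest among potential dose levels".
- **SRC timing.** Section 7.3.3 refers to scheduled meetings without an interval. The one time point given is: "The SRC will meet after all patients in the newly escalated cohort have completed the DLT evaluation period". It adds: "The SRC will also conduct unscheduled meetings on an as needed basis".
- **General monitoring.** The section headed Phase 1 Dose Escalation says: "Procedures for close monitoring of the DLT period and entire study have been established". It points to sections 12.1 and 14.1.
- **Phase 2 safety analysis.** Section 13.1.9.2.2 is descriptive. The SAP adds no toxicity rule and, in its section 2, records termination after two patients.

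**The concern.** Phase 2 is the larger part of the study, and every patient in it receives the same dose. If that dose is more toxic than Phase 1 suggested, the signal is an accumulation of events across patients. The plan sets numeric thresholds for an accumulation of responses but none for an accumulation of toxicities, and it names no Phase 2 look at which the SRC would assess them together. Planned treatment is 24 weeks after a 28-day DLT window, and cardiac toxicity and hepatotoxicity are events of special interest, so some relevant toxicity could fall outside what Phase 1 measured. At stake is how many patients are treated at an over-toxic dose before a review of accrual is triggered by rule rather than by discretion.

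**Working it through.** **1. Does any stated rule act as a Phase 2 accrual threshold?**

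| Provision | Applies in Phase 2? | Sets an aggregate toxicity count or rate? |
|---|---|---|
| Response criteria (13.1.3, 13.1.9) | Yes | No, response only |
| Enrolment suspension (7.3.4, 13.1.8.3) | Phase 1 heading; compares dose levels, and Phase 2 has one | Yes, but on the probability of the *target* interval, not of overdose |
| SRC review after a cohort (7.3.3) | No escalated cohort in Phase 2 | No |
| SRC meetings as needed (7.3.3) | Yes | No |
| Tables 4 and 5; 7.4.1; 8.3.1 | Yes | No, patient level |
| SAE and AESI reporting (12.1.6.4) | Yes | No, event level |
| Site monitoring (14.1) | Yes | No |

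No row is both applicable to Phase 2 and an aggregate toxicity threshold.

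**2. How likely is an over-toxic recommended dose on the plan's own figures?** Table 14 (Appendix 2) gives the probability of recommending a dose with a true DLT rate above 33%: 0 in A, 0.201 in B, 0 in C and 0.303 in D. Table 13 gives the context. In C every dose has a 5% rate, so 0 is automatic. In D the over-toxic doses (210 and 270 mg) both have a 35% rate, so the excess is modest. In B they run from 35% (120 mg) to 90% (270 mg), and Table 14 does not split them.

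**3. What would a simple rule do?** The documents give no Phase 2 toxicity rule to reproduce, so this is an illustration. My assumptions are a Beta(1,1) prior, looks at n = 10, 20, 30, 40 and 50, a maximum of 60, no response-based stop, and a pause when Pr(p > 0.33) exceeds a cut-off c. The 33% limit is the protocol's own over-dosing boundary.

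After x events in n patients, Pr(p > 0.33) = 1 − F(0.33; 1 + x, 1 + n − x), where F is the Beta distribution function. At n = 10, x = 4 gives 0.719, x = 5 gives 0.883 and x = 6 gives 0.963. The boundary is therefore 5 for c = 0.80 and 6 for c = 0.90. The same step at the other looks gives:

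- c = 0.80: ≥5/10, 9/20, 12/30, 16/40, 20/50
- c = 0.90: ≥6/10, 10/20, 14/30, 17/40, 21/50

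Pause probabilities follow by exact recursion, f(n, x) = (1 − p)·f(n − 1, x) + p·f(n − 1, x − 1), removing the mass at or above the boundary at each look:

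| True rate | 20% | 25% | 30% | 33% | 35% | 40% | 45% |
|---|---|---|---|---|---|---|---|
| c = 0.80 | 4% | 12% | 28% | 41% | 51% | 74% | 90% |
| c = 0.90 | 1% | 4% | 13% | 22% | 31% | 56% | 80% |

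**4. Mean enrolment at c = 0.80, if every pause ends accrual.** At a true rate of 40%, the probabilities of pausing at the five looks are 0.367, 0.135, 0.149, 0.054 and 0.034, leaving 0.261 that reach 60. So 10 × 0.367 + 20 × 0.135 + 30 × 0.149 + 40 × 0.054 + 50 × 0.034 + 60 × 0.261 = 30.4.

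That assumes accrual holds while each look is pending. If instead 6 more patients enrol during each look (an assumption), the mean rises by 6 × 0.739 = 4.4, to 34.8.

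| True rate | 35% | 40% | 45% |
|---|---|---|---|
| With holds | 39.7 | 30.4 | 22.5 |
| No hold, 6 more per look | 42.8 | 34.8 | 27.9 |

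These are best cases. A pause that ends in resumption saves less, and if every pause does, enrolment is 60.

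**The case against.** The strongest reply is that Phase 2 safety is watched closely. SAEs and cardiac or hepatic AESIs go to the sponsor within 24 hours, related or not. Table 4 requires a hold for related Grade 3 non-hematologic events, apart from a few brief exceptions, and discontinuation at Grade 4. New related events of Grade 4 or higher are to be discussed with the Medical Monitor, who sits on the SRC with the Safety Lead. All of this stands. A reader might infer from the gap that patients could accumulate before anyone has to look at safety; the documents do not support that. Nor does "If neither criterion is met, it will continue to more fully characterize the response rate" oblige the sponsor to enrol on despite toxicity: it refers to the two response criteria and does not bar the SRC from acting.

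Further points on that side:

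- **An SRC schedule may exist elsewhere.** Correct. The claim is only that these documents state none for Phase 2.
- **The RP2D is not simply a six-patient decision.** Correct. Appendix 2 also requires either more than 50% posterior probability of targeted toxicity or at least 12 patients on the trial, plus clinical review, and the model works under overdose control. An argument from six patients alone would overstate the risk, so Table 14 is used. Even there, the simulations follow the model, while the real choice adds SRC review.
- **The example rule separates poorly near 33%.** Correct: at c = 0.80 it pauses 41% of trials at 33% and 51% at 35%. Choosing a cut-off is a trade-off, and clinical SRC review without a number is a defensible position for a small open-label expansion. It still needs a stated review point.
- **The response rules are optional** ("has the option to stop the enrollment of Phase 2") and have no stated prior. These are separate efficacy-design matters and carry no weight here.

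**Conclusion.** The point holds as an omission from the design: Phase 2 has no aggregate toxicity threshold for pausing accrual and, in these documents, no SRC review point. It does not mean that safety review is absent. The protocol's simulations make an over-toxic recommended dose a real possibility in two of four scenarios (20.1% and 30.3%), although in D the excess over 33% is two percentage points.

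A simple rule would prompt review in about half to three quarters of trials at a true rate of 40% (56% or 74%, by cut-off), at the price of some pauses at acceptable rates. Those figures rest on the Beta(1,1) prior, the five looks and the 33% limit chosen here.

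A reader might also infer that patients were harmed by the gap. The SAP records termination after two patients and nothing shows that Phase 2 opened, so no effect on a Phase 2 patient is shown. The change is worth making if the design is reopened or reused.

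**What to change.** In 7.1.3, 7.3.3 and 13.1.9:

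- Have the existing SRC review Phase 2 safety when 10, 20, 30, 40 and 50 treated patients have completed 28 days or had an event, without waiting for efficacy evaluability.
- At each look, include all cardiac and hepatic AESIs to date, including those after day 28.
- Pause accrual for SRC review when Pr(rate of drug-related DLT-type events > 33%) exceeds a prespecified cut-off. State the prior, the cut-off, the boundary counts and the operating characteristics at true rates from 20% to 45%. Choose between 0.80 and 0.90 with both rows of the pause table in view.
- Count section 7.4.2 events as adjudicated by the SRC, but exclude disease-related anemia. Table 5 exempts anemia; 7.4.2 as written does not.
- State whether accrual continues while a look is pending, and what the SRC may decide: resume, lower the dose or stop.

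**Cost.** A protocol paragraph, a five-row boundary table, and SRC time for five looks and for adjudication; no new committee and no new assessments. False pauses occur in 4/12/28/41% of trials at true rates of 20/25/30/33% (0.80), or 1/4/13/22% (0.90, with less detection above 33%). There are also either up to five accrual holds of up to 28 days each (at most 5 × 28 = 140 days) or, without holds, the smaller saving in enrolment shown above.

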7.2. Planned Number of Patients

Approximately 30 patients are planned to be enrolled in Phase 1, and approximately 10-60 patients in Phase 2.

7.2.1. Patient Replacement or Addition

Patients who do not meet either of the criteria for the DLT Analysis Set, as described in [Section 13.1.5](#), may be replaced as needed to permit dose escalation.

7.3. Treatment Assignment

7.3.1. Calculation of Dose

In Phase 1, all patients will receive the dose of TP-0184 according to the cohort in which they are enrolled ([Table 3](#)).

Table 3: Planned Dose Escalation Levels

Dose Level	Dose (Daily Schedule)
-1	10 mg
1	20 mg
2	40 mg
3	60 mg
4	90 mg
5	120 mg
6	160 mg
7	210 mg
8	270 mg

Note: An intermediate dose level between the planned dose levels may be explored. In addition, based on a safety evaluation during the escalation phase, additional dose schedules than those outlined in the table may be explored after discussion and concurrence with SRC members and SDP Oncology clinical team.

Intra-patient dose escalation is not permitted in this protocol.

In Phase 1 and 2, patients will be treated for 24 weeks (6 cycles) and based on assessment of response, continue to receive TP-0184 in the absence of MDS disease progression or until loss of hematological response or unacceptable toxicity.

Note: Loss of hematological response (lack of response or refractory to further treatment) will follow the guidelines for progression/relapse after hematological improvement by IWG Response Criteria for MDS 2006 ([Appendix 6](#)).

7.3.2. Description of Dose Escalation Study

7.3.1. Phase 1 Dose Escalation

Dose escalation will be performed using a design based on a 2-parameter BLRM ([Neuenschwander 2008](#)). The BLRM method will be applied along with the escalation with overdose control (EWOC) principle to control the risk of exposing patients to toxic doses ([Babb 2013](#)). Based on this principle, a dose level will be considered safe if the probability of excessive toxicity (ie, the probability of a DLT rate over 33% is no greater than 25%). The MTD with estimated posterior probability of a DLT within target toxicity interval (16%, 33%) among the admissible doses fulfilling EWOC is determined by BLRM. The MTD is estimated based on observed DLTs.

The use of Bayesian adaptive models for Phase 1 studies has been advocated by the European Medicines Agency's guideline on clinical trials in small populations ([European Medicines Agency, 2016](#)).

The actual dose level to be tested in the next cohort will be chosen based on the above risk assessment, using the BLRM method. The dose recommended by the BLRM method will be treated as guidance and will be integrated with a clinical assessment of the safety adverse event information and review of clinical data, including above safety and PK data. Intermediate doses between planned dose levels may be SDP Oncology explored based on safety consideration after discussion and concurrence with SRC members and SDP Oncology clinical team. The BLRM method estimates the MTD by updating the probability of observing a DLT for each dose level in the study as DLT information becomes available. An additional cohort with a different dose schedule may be considered based on clinical judgment supported by medical observations.

Procedures for close monitoring of the DLT period and entire study have been established ([Section 12.1](#), [Section 14.1](#)). In addition, an SRC will conduct scheduled meetings and will provide safety oversight of the patients, determine DLTs, and guide escalation and dose decisions ([Section 7.3.3](#)).

7.3.2. Determination of RP2D

The RP2D is determined based upon safety, PK, pharmacodynamic, efficacy and other available data. Determination of the RP2D will be performed in consultation with the SRC members based on safety and other data available at the time of the RP2D decision. In the Phase 2 portion of the study, the RP2D, as determined in Phase 1, will be used.

7.3.3. Safety Review Committee

The SRC will consist of the Investigators, the Safety Lead, the Statistician, and the Medical Monitor, and a cardiologist consultant. The SRC will conduct scheduled meetings and will provide safety oversight of the patients, determine DLTs, and guide escalation and dose decisions. The SRC will meet after all patients in the newly escalated cohort have completed the DLT evaluation period and before proceeding with the next cohort at a higher dose level.

The SRC will review and assess all available safety data from each cohort, together with available PK and pharmacodynamic data, to determine the escalation to the next dose level cohort. The SRC will also conduct unscheduled meetings on an as needed basis to review other information that may be relevant to the conduct of this study or safety of the patients.

7.3.4. Phase 1 Study Stopping Rules

Dose escalation can be stopped earlier by a joint decision from the SDP Oncology clinical team and the Investigators during a SRC meeting, by considering the model estimations and a global assessment of the safety, PK, pharmacodynamics, and preliminary activity data.

The following safety event will trigger a temporary suspension of patient enrollment to study treatment:

- The posterior probability of target toxicity at each dose level exceeds 50% and is the highest among potential dose levels.

Based on the safety review by the SRC members and the SDP Oncology clinical team, it will be determined whether the study may continue (with or without a protocol amendment) or if it must be terminated.

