13.1.8.3. Phase 1 Study Stopping Rule

Dose Escalation can be stopped earlier by a joint decision from SDP Oncology and the Investigators during an SRC meeting, by considering the model estimations and a global assessment of the safety, PK, pharmacodynamics, and preliminary clinical data.

The following safety event will trigger a temporary suspension of patient enrollment to study treatment if the posterior probability of target toxicity at each dose level exceeds 50% and is the highest among potential dose levels.

Based on the safety review with the SRC, SDP Oncology will determine whether the study may continue (with or without a protocol amendment) or if it must be terminated.

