20.1.1.3. Dose Recommended by the BLRM Method

The dose allocation will start at the dose of 20 mg. Patients will be included by cohort of 1 to 6 patients. There must be at least 3 DLT evaluable patients at a specific dose level if there is a DLT observed in that level. After each cohort of patients is completed, the dose recommendation by the model will be based on posterior summaries including the mean, median, standard deviation, 95% credible interval, and the probability that the true DLT rate for each dose lies in one of the following categories:

- (0, 16%]: under-dosing
- (16%, 33%]: targeted toxicity
- (33%, 100%]: over-dosing

Following the principle of EWOC, after each cohort of patients the recommended dose by the model is the one with the highest posterior probability of the DLT rate falling in the targeted toxicity interval (16%, 33%] among the admissible doses fulfilling EWOC, i.e., it is unlikely (< 25% posterior probability) that the DLT rate at the dose falls in the over-dosing interval.

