17.2.2 Final Recommendation and Stopping Rules

Dose escalation will continue until identification of the MTD(s) or suitable lower dose for recommended phase 2 dose(s) (the RP2D). This will occur when the following conditions are met:

1. At least 6 patients have been treated at this dose.
2. This dose satisfies one of the following conditions:
 - a. The posterior probability of targeted toxicity at this dose exceeds 50% and is the highest among potential doses, or
 - b. A minimum of 12 patients have already been treated on the trial.
3. It is the dose recommended for patients, by review of all clinical data by patients of the end of cohort meeting. Of note, the Dose Escalation part could be stopped earlier by a joint decision from the Sponsor and the Investigators during an SRC meeting, by considering the model estimations and a global assessment of the safety, PK, pharmacodynamics, and preliminary activity data.

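### The only mandatory numerical Phase 1 suspension trigger is set on target toxicity, the condition that identifies the MTD, and not on over-dosing

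*Protocol*

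**What the plan says.** Protocol 7.3.4 lists one safety event that suspends Phase 1 enrollment: "The posterior probability of target toxicity at each dose level exceeds 50% and is the highest among potential dose levels". Section 13.1.8.3 repeats it; the event will "trigger a temporary suspension of patient enrollment to study treatment if the posterior probability of target toxicity at each dose level exceeds 50" percent and is the highest. After a suspension, "it will be determined whether the study may continue (with or without a protocol amendment) or if it must be terminated".

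Section 20.1.1.3 (Appendix 2) splits the DLT rate into three bands: up to 16% is under-dosing, the middle band is "16%, 33%]: targeted toxicity", and above 33% is over-dosing. EWOC admits a dose only if "it is unlikely (< 25% posterior probability) that the DLT rate at the dose falls in the over-dosing interval".

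Appendix 2, 17.2.2, uses almost the same words as the trigger for a different purpose. Condition 2a for identifying the MTD or RP2D is "The posterior probability of targeted toxicity at this dose exceeds 50% and is the highest among potential doses".

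The other safeguards carry no suspension number. Section 7.3.1 (Phase 1 Dose Escalation) treats the model's recommendation as guidance. Section 7.3.3 provides that "The SRC will meet after all patients in the newly escalated cohort have completed the DLT evaluation period" and before the next higher dose opens. Section 7.3.4 allows, but does not require, an earlier stop by joint decision.

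**The concern.** A suspension rule labeled as a safety event should respond to evidence of over-dosing. This one is written on the outcome the escalation is trying to find. If the lowest doses prove too toxic, the case for which a mandatory pause matters most, the documents contain no numerical rule that requires one. Nor do they say that enrollment pauses when no dose satisfies EWOC. Whether to continue is then left to judgment.

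**Working it through.** **Inputs.** The model is logit π(d) = log α + β·log(d/90) with β > 0 (Appendix 2, Statistical Model). The Table 11 prior for (log α, log β) has means (−0.847, 0.913), SDs (1.275, 0.482) and correlation −0.9. Doses run from 10 mg (level −1) to 270 mg. Below, P(over) = P(DLT rate > 33%) and P(target) = P(16% < DLT rate ≤ 33%). A dose is inadmissible when P(over) is 25% or more. Posteriors come from numerical integration on a grid.

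**Reproducing Table 12.** Prior P(over) at 20, 40, 60, 90 and 120 mg is printed as 0.0571, 0.1395, 0.2448, 0.4578 and 0.7519. Recomputed values are 0.0587, 0.1378, 0.2426, 0.4582 and 0.7474, all within half a percentage point.

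**Literal reading.** The condition would have to hold at each dose, and each dose would have to be the highest. Only one dose can be, so it is never met.

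**Any-dose reading, bound.** Since β > 0, π(d) rises with dose, so P(over) at any dose is at least P(over) at the lowest dose. Hence, for every d,

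P(target at d) ≤ 1 − P(over at d) ≤ 1 − P(over at lowest dose).

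If P(over) at the lowest dose is 50% or more, no dose can have P(target) above 50%.

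**First cohort at 20 mg.** Of all outcomes with 1 to 6 patients, these 12 leave no admissible dose, even 10 mg:

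| DLTs/patients | P(over) 10 mg | P(over) 20 mg | Highest P(target), any dose |
|---|---|---|---|
| 1/1 | 0.27 | 0.46 | 0.24 |
| 2/2 | 0.54 | 0.76 | 0.25 |
| 2/3 | 0.34 | 0.61 | 0.31 |
| 3/3 | 0.72 | 0.90 | 0.20 |
| 3/4 | 0.53 | 0.81 | 0.30 |
| 4/4 | 0.84 | 0.96 | 0.13 |
| 3/5 | 0.37 | 0.70 | 0.37 |
| 4/5 | 0.69 | 0.91 | 0.24 |
| 5/5 | 0.91 | 0.99 | 0.08 |
| 4/6 | 0.53 | 0.84 | 0.34 |
| 5/6 | 0.80 | 0.96 | 0.17 |
| 6/6 | 0.95 | 0.995 | 0.05 |

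The trigger is met in 0 of 12. With a second cohort of 3 to 6 at an admissible 10, 20 or 40 mg, it is met in 6 of 162 outcomes that leave no admissible dose (P(target) at 10 mg 0.51 to 0.52).

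**On-target data.** After 0/3 at each of 20, 40 and 60 mg (EWOC satisfied at each step; P(over) at 90 mg is 0.15 before dosing there and 0.195 after 1/3), the 90 mg posteriors are:

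- 2/6: P(target) 0.54, P(over) 0.23
- 2/9: 0.54, 0.11
- 3/12: 0.61, 0.13

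All three meet the trigger. It can also be met incidentally at an over-toxic dose: 1/3 at 120 mg after 0/12 below gives 0.53 with P(over) 0.40. Table 15 scenario 4 prints P(target) 0.5059 for 1/4 at 90 mg, but this recomputes to 0.47 and is not relied on.

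**Simulation** (cohorts of 3 from 20 mg, no level skipped upward, at most 30 patients; the low-dose toxic rates are assumptions, since the documents give none).

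- Trials end when no dose is admissible or when Appendix 2's conditions 1 and 2 are met. For true rates at 10/20 mg of 40/50%, 50/50% and 60/70%, 79%, 86% and 99% of trials run out of admissible doses. The trigger was ever met in 5.6%, 6.3% and 1.1% of those.
- Trials end only when no dose is admissible or at 30 patients, with all trials as denominator. For 35/45%, 40/50%, 50/60% and 60/75%, the trigger is ever met in 35%, 24%, 9% and 1%.
- Table 13 scenarios A, B, C, D (5% assumed at 10 mg), with the first end rule. It is met at an admissible dose in 20%, 19%, 5% and 17% of trials, but in only about 1% to 2% before Appendix 2's end conditions are met.

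**The case against.** The strongest reply is that patients are not unprotected. Section 13.1.8.1 has the Safety Review Committee (SRC) decide after each escalation cohort, using the model with EWOC. Section 7.3.3 allows unscheduled meetings. Sections 7.3.5 and 7.4.2 take any patient with a Cycle 1 DLT off treatment. Appendix 2's closing paragraph says that more than 1 DLT in 3 patients leads to a lower dose or the same dose. A bad first cohort would therefore most likely go to the committee and not be followed by unchecked enrollment. All of that stands, but none of it is a mandatory numerical suspension. The closing guidance also offers options that EWOC rejects: after 2/3 at 20 mg, P(over) is 0.61 at 20 mg and 0.34 at 10 mg.

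A reader might infer that the trigger is nearly always silent whenever the low doses are too toxic. That goes too far. For true 10 mg rates of 35% to 40% it fires in 24% to 35% of trials when the trial stops at the first point with no admissible dose, and in about 64% to 80% if enrollment ran on at 10 mg to 30 patients regardless. Those firings occur because the data look on target, so they limit the claim without rescuing the rule.

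A reader might also infer that the rule would halt a successful trial. The documents do not support that. The suspension is temporary, arises only under the any-dose reading, and nearly always coincides with the point at which Appendix 2 would end escalation anyway.

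Finally, SAP Section 2 reports that the study ended after two patients and reduces the analysis to listings, so no result changes.

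**Conclusion.** The concern holds: the trigger uses the wrong toxicity interval. Under the literal reading it is inert. Under the any-dose reading it tracks on-target dosing, and once over-dosing at the lowest dose is at least as likely as not, it cannot be met at all. That last result is arithmetic and needs only β > 0. The 0 of 12 count rests on the Table 11 prior and on taking 10 mg as the lowest dose. The simulated rates rest further on the assumed toxic rates, cohorts of 3 and the end rules stated above. The consequence is a missing mandatory pause, partly covered by discretionary review. It is worth correcting as a design rule, although its practical effect in this study was limited.

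**What to change.** In 7.3.4 and 13.1.8.3, replace the condition with: *P(DLT rate > 33%) at dose level −1 (10 mg), the lowest planned dose, exceeds 25%, so that no planned dose satisfies EWOC, assessed once at least 3 DLT-evaluable patients have been treated in total.* Naming 10 mg matters because Appendix 2's prior and scenario tables start at 20 mg. Keep the target-toxicity condition only as 2a in Appendix 2. Add to Appendix 2's closing paragraph that the decrease-or-stay guidance applies only while an EWOC-admissible dose remains.

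The cost is amendment wording in three places. No patients or data are added, because the model already gives the over-dosing probability. The 3-patient floor is in line with the existing requirement that "There must be at least 3 DLT evaluable patients at a specific dose level if there is a DLT observed in that level", and it prevents a pause after 1/1 (P(over) at 10 mg 0.27). After 2/2 (0.54) the rule waits for a third patient unless the SRC pauses at its discretion.

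The downside is a temporary pause after 2 or more DLTs in 3 patients at 20 mg, before 10 mg has been tried. With X ~ Bin(3, p), P(X ≥ 2) = 3p²(1 − p) + p³:

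- p = 5%: 0.7%
- p = 25%: 16%
- p = 30%: 22%
- p = 50%: 50%
- p = 70%: 78%

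The 25% and 30% rates lie inside the target band, so some pauses will prove unnecessary; the SRC may then resume at 10 mg. Outcomes 2/4, 2/5, 2/6 and 3/6 at 20 mg do not pause (P(over) at 10 mg 0.20, 0.12, 0.07, 0.24). In the simulated Table 13 scenarios the new rule is met in 0.7% to 0.8% of trials.
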